4 STUDY POPULATION

4.1 Selection of Study Population

Patients may be referred to OUS from all surgical or oncological departments in Norway. Systemic chemotherapy will be administered according to standard procedure at the local oncological departments. Administration of HAI-treatment will be performed at OUS. Liver resection and liver transplantation will be performed at OUS.

Palliative systemic 2nd line chemotherapy is standard of care for patients eligible for inclusion in this study. Liver transplantation is not considered standard treatment option for CRC patients neither in Norway nor internationally. Documented benefit of liver resection has not been established in this cohort of CRC patients. If HAI-treatment improves survival in this cohort of patients has not been well documented. Patients included in this study may have the benefit of extended overall survival compared to standard palliative chemotherapy only, although liver transplantation or liver resection may result in serious complications in a small fraction of patients.

4.2 Number of Patients

Forty-five patients will be included in this trial.

4.3 Inclusion and exclusion criteria

4.3.1 Inclusion *Excalibur 1 and 2*

Included patients must fulfil the following criteria

1. Primary histology:
 - a. Verified adenocarcinoma in colon/rectum, radically resected with adequate margins/pre-operative treatment
2. Liver metastases:
 - a. Six or more liver metastases that have progression (or insufficient response on 1st line chemotherapy, including toxicity). and are hence planned for 2nd line chemotherapy
3. If a history of confirmed extra hepatic metastatic lesion or local relapse, this must have been successfully treated more than 2 years ago without a new relapse.
4. Chemotherapy
 - a. Planned for 2nd line chemotherapy.
 - b. If patients are switched to 2nd line chemotherapy, randomization can only be allowed prior to first evaluation on 2nd line chemotherapy regimen.
5. The patient
 - a. Good performance status, ECOG 0 or 1.
 - b. Satisfactory blood tests: Hb >10g/dl, neutrophils >1.0 (after any G-CSF), TRC >75, Bilirubin <1.5 x upper normal level, ASAT, ALAT <5 x upper normal level, Creatinine <1.25 x upper normal level. Albumin above lower normal level.
 - c. Women of childbearing potential (WOCBP) must have a confirmed menstrual cycle and a negative highly sensitive pregnancy test prior to inclusion, or two negative pregnancy tests two weeks apart
 - d. WOCBP must agree to use a highly effective method of contraception (see section 6.1.2) for the entire period of exposure to the IMP in the trial, plus for one menstrual cycle/30 days after the last exposure due to the genotoxic potential of the IMP
 - e. Men that may have sexual relations with a WOCBP during the trial must agree to use a condom during intercourse for the entire period of exposure plus for one sperm cycle / 90 days after the last exposure due to the genotoxic potential of the IMP
6. Signed informed consent and expected cooperation of the patients for treatment and follow up must be obtained and documented according to GCP, and national/local regulations.

Exclusion Criteria *Excalibur 1 and 2*

Any of the following criteria will exclude participation in the trial:

1. Arterial anatomy not suited for HAI pump-line insertion.
2. Liver metastatic ingrowth to the diaphragm determined by CT-scan and/or MRI/or ultrasound
3. Previous bone or CNS metastatic disease.

4. Non-curable pulmonary or peritoneal metastases, non-regional lymph-nodes, or local recurrence on PET/CT scan, and on CT or MRI thorax/abdomen/pelvis dated within 6 weeks prior to the trial hospital MDT meeting.
5. Patients with known intolerance or allergy to any ingredient of the IMP to be used as standard therapy for that patient must be excluded
6. Breastfeeding women must be excluded
7. Patients with a psychiatric condition that makes participation in the trial impossible or unethical
8. Patients in a poor nutritional state, those with depressed bone marrow function or those with potentially serious infections must be excluded.
9. Any other reason why, in the opinion of the investigators, the patient should not participate.

Exclusion Excalibur 1

Any of the following will preclude inclusion into Excalibur 1 (but not into Excalibur 2)

1. BRAF positivity
2. Any sign of extra-hepatic metastatic disease or local recurrence on PET/CT scan, and on CT or MRI thorax/abdomen/pelvis dated within 6 weeks prior to the trial hospital MDT meeting (exception allowed for ≤ 3 resectable lung lesions all ≤ 15 mm).
3. Liver lesion >10 cm
4. Patient BMI > 30
5. Any previous non colorectal malignancy within latest five years
6. Age ≥ 70 years

5 TREATMENT

For this study the drugs that are used for HAI are fluorodeoxyuridine also known as floxuridine (FUDR, Fresenius Kabi, LLC, USA) and dexamethasone. These drugs are defined as Investigational Medicinal Product (IMP). The patients will receive 20 mg proton pump inhibitor.

All patients will receive second line standard systemic chemotherapy at the discretion of the treating medical oncologist. Resection in the HAI and standard care groups will be undertaken only provided sufficient response on 2nd line chemotherapy (with or without HAI/FUDR) has been achieved (defined as ≥ 10 % response on median diameter of two target lesions, i.e. measured as with RECIST 1.1. but with a trial-specific cut-off). The study is a three- armed study, where the control arm receives systemic 2nd line chemotherapy only, one arm receive systemic chemotherapy and HAI and the third arm 2nd line systemic chemotherapy and liver transplantation.

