5.1 Technical procedures

5.1.1 Second line systemic chemotherapy

The medical oncologist at the local hospital who knows the patient's response and side-effects of first line chemotherapy will decide on second line chemotherapy and schedule the treatment. If the patient is randomized to HAI, the systemic chemotherapy will have to be given according to the planned HAI schedule. Study nurse at OUS will be responsible for coordinating HAI treatment and systemic treatment

Patients randomized to liver transplantation or systemic chemotherapy (and resection if possible) will have transplantation/resection when the MDT-meeting considers surgical treatment possible. All patients will receive chemotherapy at their local oncological departments. Dose reduction/dose delay will be administered according to standard procedure at the different treating oncological departments. Depending on logistics, some patients in the HAI group will have commenced 2nd line chemotherapy prior to insertion of the pump.

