5.5 Schedule of events

- Identification
 - Patients are identified from referrals or during MDT-meetings by surgeon or oncologist.
 - A trial specific MDT evaluation of liver metastases and resectability is performed.
 - Following this MDT-meeting, the patient is invited for out-patient visit within 10 days.
 - If no updated high-quality thoracic/abdominal CT and MR scan is available (No older than 4 weeks by date of out-patient visit), these are booked.
- At out patient clinic:
 - Eligibility for *Excalibur* 1 or 2 is assessed.
 - In house review of new images if applicable.
 - Eligible patients receive written and oral information about the trial and risks pertaining to HAI-catheter insertion/transplant/systemic chemotherapy
 - Measurement of CEA and standard blood chemistry
 - If patient consents:
 - Baseline QoL survey (C30) and EQ5D questionnaire is completed
 - Patient's latest CT or MRI scans are referred to next MDT meeting for designation of three target lesions for RECIST evaluation
 - Availability of mutation status is confirmed. If mutation status is not already performed, this is ordered from pathology lab.
 - Decision of eligibility for *Excalibur* 1 or 2 is decided by two trial investigators. If a patient is found to be eligibility for *Excalibur* 1 a member of transplant team will concur and provide specific information about transplants.
 - If a patient has begun or is planned for 2nd line chemotherapy, the randomization MUST take place before any evaluation of 2nd line treatment effect, i.e imaging (CT/MR). (PET for evaluation of extra hepatic disease is allowed). The choice of drugs for 2nd line chemotherapy must be decided on prior to randomization.
 - Inclusion is confirmed
 - Patient card
 - The following appointments are booked within two weeks:
 - A PET scan following 4 week chemo abstinence. If the patient has recently received systemic chemotherapy, a 4 week chemo abstinence must be ensured and randomization may need to be somewhat delayed.
 - Patients eligible for *Excalibur* 1 for individual assessment by transplant team
 - An operation theatre for insertion of HAI-pump catheter at four weeks from inclusion
- PI meeting two weeks following inclusion:
 - Documents, inclusion details, transplant assessment and PET results are reviewed

- If satisfactory, a web-based randomization is performed.
- All patients:

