 - Monthly pregnancy testing should be performed in women of childbearing potential (WOCBP) as long as they receive chemotherapy according to study protocol. This can be done with a urine test at home combined with contact with the study team by phone
 - A calendar for oncologist visits and provision of systemic chemotherapy is created by coordinating nurse. Control scans are ordered for each 2nd month for the first year following randomization and as long as the patients receive chemotherapy, each 3rd month for the second year and each 6th month for the third year. MDT meetings are scheduled for one week following each new scanning to assess response and possible resectability
 - Out-patient control appointments are scheduled for outcome assessment including QoL-scoring (3, 6, 9, 15, 18, 21 and 24 months)
- Patients in HAI group (group 2 a and 2b)
 - A calendar of reservoir refills is created and harmonized with provision of systemic treatment.
 - A laparotomy is performed within 2 weeks from randomization with insertion of catheter and reservoir for HAI-pump.
- Patients in transplant group
 - Oncologists are instructed to avoid Avastin in systemic chemotherapy while the patient is listed.

Table 3: Overview of screening procedures, End of study/Withdrawal

Overview of screening procedures, End of study Withdrawal												
Item	ICF	Inc/Ex	Med Hist	Prior Trea	Phys Exam	Vit Sign	ECOG	CT/ MR	QoL	Blood Sample	Adverse Event	Survival Assessment
Screening	x	x	x	x	x	x	x	x	x	x	x	
EOS/Withdrawal											x	x

Table 4: Calendar of cycles and events for patients in HAI group

Calendar of cycles and events for patients in HAI group								
Day cycle 1 + 2	1	2	15	16	29	30	44	
Day cycle 3 + 4	61	62	75	76	89	90	104	
Pump refill FUDR at OUS	x				x			
Pump refill HepNaCl at OUS			x					x
Systemic chemo local hospital		x		x		x		

Table 5: Calendar of cycles and events for patients in control group and on waiting list for LTx-group

Calendar of cycles and events for patients in control group and on waiting list for LTx- group							
Day cycle 1 + 2	1		15		29		44
Day cycle 3 + 4	61		75		89		104
Systemic chemo local hospital	x		x		x		x

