5.6 By Visit

Informed consent

Informed consent will be obtained voluntarily by each subject before any study specific procedures are initiated. Patients will be given information about inclusion in the study at the out-patient clinic at Rikshospitalet, Oslo University Hospital.

The following tests will be done at screening:

Clinical status

A medical history will be recorded, including disease history and corresponding treatment details, physical examination e.g. cor/pulm/abdomen and peripheral lymph node status), vital signs (weight, blood pressure, temperature and pulse) and ECOG performance status.

Tumor evaluation: CT thorax/abdomen (pelvis) and MRI-liver within 4 weeks of MDT-meeting at Rikshospitalet. All patients included in the study will receive systemic chemotherapy as standard of care. This treatment will be given at local hospitals and as standard of care blood chemistry will be performed before administration of chemotherapy. Patients randomized to HAI will in addition have blood chemistry the day the pump is filled for a new 14-day treatment. The safety measures for the systemic chemotherapy will be standard of care and documented in the patient records according to standard procedures at the different hospitals. CT (MRI)-scans will be performed at local hospital and the CT (MRI) scans showing stable disease or response will be submitted to the HPB-meeting at Rikshospitalet for evaluation of resectability. Resectable patients (from both the control and HAI groups) will have liver resection at Rikshospitalet.

Laboratory analysis

Blood samples will be taken to determine CRP, Hb, HCT, WBC (incl.differential counting), PLT, Na, K, Ca, creatinine, ASAT, ALAT, LD, ALP, γ GT, INR, albumin, bilirubin CEA and CA 19-9. Pregnancy test will be secured within the last 14 days in fertile women.

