5.6.1 Before Treatment Starts

Eligible and consenting patients will be randomized. Patients randomized to systemic chemotherapy will receive chemotherapy at their local hospital. Patients randomized to HIA and systemic chemotherapy will have the pump placement and HAI administration at the department of gastrointestinal surgery/HPB section at OUH/Rikshospitalet. The systemic chemotherapy will be administered at local hospitals. The patients in these two groups will repeatedly be evaluated for liver resection at the MDT-meeting at Rikshospitalet and patients who become resectable will have liver resection/local ablation at Rikshospitalet. Patients randomized to liver transplantation will be evaluated for liver transplantation and receive liver transplantation according to standard procedure at the department of Transplantation Medicine, Rikshospitalet. These patients will receive chemotherapy at their local hospital until time of receiving a liver transplant.

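### Resection in the HAI and control arms depends on a response threshold in one section and on resectability alone in three others, and the lesions behind the threshold are not fixed

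*Protocol*

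**What the plan says.** **The condition.** Section 5 (Treatment) sets a necessary condition for both non-transplant arms: "Resection in the HAI and standard care groups will be undertaken only provided sufficient response on 2nd line chemotherapy". Sufficient is defined as at least 10% "response on median diameter of two target lesions, i.e. measured as with RECIST 1.1. but with a trial-specific cut-off". Section 5.6.4 echoes this when it speaks of HAI patients whose response was not sufficient for resection.

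**The route to surgery elsewhere.** Three other places omit the condition:
- Section 5.1.1 says that patients in the control and transplant arms "will have transplantation/resection when the MDT-meeting considers surgical treatment possible".
- Section 5.6 says: "Resectable patients (from both the control and HAI groups) will have liver resection at Rikshospitalet".
- Section 5.6.1 says of the same two arms that "patients who become resectable will have liver resection/local ablation at Rikshospitalet". In these sections, ablation is mentioned only here.

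**The lesions.** Section 5.5 refers the baseline scans to the MDT for "designation of three target lesions for RECIST evaluation".

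**The routing of scans.** Section 5.5, under the items for all patients, says: "MDT meetings are scheduled for one week following each new scanning to assess response and possible resectability". Section 5.6 has scans done at the local hospital and says that "scans showing stable disease or response will be submitted to the HPB-meeting at Rikshospitalet for evaluation of resectability".

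**Use of the result.** Resection rate is a secondary endpoint (Table 1) and is compared between the HAI and control arms (section 8.5.2). The synopsis describes the trial as open label, and section 5.10 says that response reading cannot be blinded because the catheter is visible on CT.

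**The concern.** A patient who is technically resectable and whose target lesions have shrunk by 5% is barred from resection by section 5. Read literally, sections 5.6 and 5.6.1 have the same patient resected. The protocol ranks neither text above the other, so the decision rests on which section the treating team has in mind.

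The team knows the arm. If the threshold is enforced in one arm and passed over in the other, the difference appears in the resection rate as a treatment effect. It may also reach the primary endpoint, because section 10 links HAI to a greater chance of resection and to better overall survival. An operation done or withheld under an inconsistent rule cannot be undone at analysis. The rule decides treatment, so it belongs in the protocol and not in a statistical analysis plan.

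**Working it through.** The plan gives no figure for this point that could be reproduced. The check sets the sections side by side and adds two short calculations.

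**1. Who may be resected**

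| Section | Arms | Basis for resection | Response threshold |
|---|---|---|---|
| 5 | HAI, control | response on 2nd line | at least 10%, two lesions |
| 5.6.4 | HAI | sufficient response (implied) | no figure given |
| 5.1.1 | control (with transplant) | MDT judgement | none |
| 5.6 | HAI, control | resectable | none |
| 5.6.1 | HAI, control | becomes resectable (resection or ablation) | none |

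For the control arm, three sections omit the threshold. For the HAI arm, two do, since section 5.1.1 does not name HAI in that sentence.

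**2. Whether the threshold can be applied as written**

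Inputs: a 10% threshold on two lesions (section 5) and three designated lesions (section 5.5). The lesion sizes are invented for illustration: 30, 30 and 30 mm at baseline; 26, 27 and 30 mm at follow-up.

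Percentage change = (follow-up - baseline) / baseline.

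- First and second lesions: the median of two values is their mean, so (26.5 - 30)/30 = -11.7%. The sum gives the same, (53 - 60)/60 = -11.7%. Meets 10%.
- First and third: (28 - 30)/30 = -6.7%. Does not meet it.
- Second and third: (28.5 - 30)/30 = -5.0%. Does not meet it.
- Sum of all three: (83 - 90)/90 = -7.8%. Does not meet it.
- Median of all three: (27 - 30)/30 = -10.0%. Exactly at the threshold.

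With two lesions the choice between median and sum is immaterial. With three it is not, and the choice of pair alone can reverse the decision.

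**3. Which scans reach the trial hospital meeting**

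Section 5.5 takes every scan to an MDT meeting. Section 5.6 forwards scans that show stable disease or response, so a scan read locally as progression need not be forwarded. Both cannot describe the same process. Section 5.6.1 adds that both arms are repeatedly evaluated at the trial hospital MDT, which agrees with section 5.5.

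**4. Scale**

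Section 8.1 plans 18 patients in each of the HAI and control arms. One patient is 1/18 = 5.6 percentage points of that arm's resection rate.

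For survival, an assumption is needed. Take 2-year survival as 30% without resection (section 8.1's control figure, borrowed for this purpose) and 70% to 90% with it (assumed). One patient whose resection turns on the wording then moves the arm's expected 2-year survival by (0.70 - 0.30)/18 = 2.2 points to (0.90 - 0.30)/18 = 3.3 points. This shows scale only and estimates no bias.

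**The case against.** The strongest reply is that the sections fit together. Section 5 is worded as a necessary condition, section 5.6.4 repeats the idea, and section 5.6 only sends scans for evaluation, which is triage. The cut-off is 10%. Taking the RECIST partial-response boundary as 30% (the protocol cites RECIST 1.1 without reproducing it), patients with 10% to 29% shrinkage are classed as stable, so stable scans have to be forwarded. The statements that resectable patients will have surgery may be there mainly to say where it is done. The three lesions may serve the RECIST response-rate endpoint, with the two being a subset.

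Much of this stands. It is a reasonable reading and may be the intended one. It does not settle the matter: the unconditional sentences remain, stable disease also covers shrinkage below 10%, no precedence is stated, and no text says which two of the three lesions count. Whether ablation counts in the resection rate could be left to a statistical analysis plan. Whether it is subject to the response condition could not.

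Three stronger readings are tempting, and the documents do not support them.
- **That control patients alone are scanned locally and so filtered out before review.** Section 5.6 places scanning at local hospitals without naming an arm, and section 5.6.1 has both arms repeatedly evaluated at the trial hospital. Only pump care is specific to the HAI arm. A filter on progression would also rarely remove a patient with a 10% response, apart from local misreading.
- **That a large share of each arm is affected.** This would need the distribution of size change and the proportion technically resectable, and the protocol gives neither. Patients have six or more metastases, and section 1.7 expects response in only a small minority, so the number could be small.
- **That the rule will be applied differently by arm.** The wording permits this. Nothing shows that it is planned or likely.

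**Conclusion.** The inconsistency is real. Section 5 imposes a response condition that sections 5.1.1, 5.6 and 5.6.1 omit, with no order of precedence. The condition uses two lesions where three are designated, scan routing is described in two incompatible ways, and the standing of ablation is unstated. In an open-label trial with unblinded response reading, this leaves room for unequal application in an endpoint compared between arms and in a pathway to the primary endpoint.

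The size can be stated only per patient: 5.6 percentage points of resection rate with 18 per arm and, under the assumed survival figures, 2.2 to 3.3 points of 2-year survival. The number of patients affected cannot be derived from the documents. The text conflict depends on none of these figures. The point should be fixed, but it does not invalidate the design: a coherent reading exists, and the primary analysis is all-cause survival by intention to treat.

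**What to change.** Reconcile sections 5, 5.1.1, 5.5, 5.6, 5.6.1 and 5.6.4 into:
- one resection rule, stated once, cross-referenced elsewhere and applied identically in the HAI and control arms;
- one lesion count and one summary measure, with the lesions that feed the rule identified at baseline;
- one scan-routing rule for both arms;
- a statement of whether ablation falls under the rule and whether it counts in the resection rate.

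Whether a threshold applies, at what level, and which routing is used are clinical choices for the sponsor. The statistical requirement is that there be one rule, the same in both arms.

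At each review, record the measured percentage change and the MDT's decision. If a response condition is kept, report by arm the number meeting it beside the number resected, so that a reader can see whether it was applied evenly.

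The cost is protocol wording, submitted as an amendment under section 9.3, and a short entry in the MDT record. Section 5.5 already schedules a meeting after each scan, so recording adds no visit, scan or reader.

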5.1 Technical procedures

5.1.1 Second line systemic chemotherapy

The medical oncologist at the local hospital who knows the patient's response and side-effects of first line chemotherapy will decide on second line chemotherapy and schedule the treatment. If the patient is randomized to HAI, the systemic chemotherapy will have to be given according to the planned HAI schedule. Study nurse at OUS will be responsible for coordinating HAI treatment and systemic treatment

Patients randomized to liver transplantation or systemic chemotherapy (and resection if possible) will have transplantation/resection when the MDT-meeting considers surgical treatment possible. All patients will receive chemotherapy at their local oncological departments. Dose reduction/dose delay will be administered according to standard procedure at the different treating oncological departments. Depending on logistics, some patients in the HAI group will have commenced 2nd line chemotherapy prior to insertion of the pump.

